2.1 Study Hypotheses

The primary study hypothesis is that the Phoebe contact lens performs substantially equivalent to the MyDay contact lens for ocular health.

The secondary study hypothesis is that The Phoebe contact lens is not inferior to the MyDay contact lens for vision and visual acuity.

[REDACTED]

- [REDACTED]
- [REDACTED]

[REDACTED]

3 Study Design

This will be a double-masked, randomized, bilateral, cross-over, 3-day dispensing study comparing the Phoebe Test lens against the MyDay Control lens. Each subject will be randomized to wear either the Test or Control lenses first as a matched pair. Each lens pair will be worn for 3 days. All lenses will be replaced daily.

It is anticipated that this study will involve up to 4 scheduled visits:

- Visit 0: Enrolment / Screening / Baseline Visit
- Visit 1: Dispensing of Pair 1
- Visit 2: Follow-up of Pair 1 (+2 days) and Dispensing of Pair 2
- Visit 3: Follow-up of Pair 2 (+2 days) and Exit

4 Ethics Review / Statement of Compliance

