7.4.2 Visit 1: Dispensing visit

Dispensing visit may occur on same day as Visit 0. In which case, steps 1,2 &3 are redundant.

1. Entrance distance HHHC VA (OD, OS) with best spherocylindrical correction.
2. Slit lamp biomicroscopy will be assessed according to the criteria set out in the Appendix 2.
 - a. Not required if done in combination with Visit 0.
3. The investigator will confirm that the patient meets the criteria set out in the inclusion criteria.
4. The first pair of lenses will be inserted by the subject according to randomization schedule.
5. Initial contact lens power chosen based on vertexed, spherical equivalent obtained from refraction.
6. The initial lens fit will be assessed for fit acceptance (acceptable or not acceptable). If the fit is acceptable, the subject will be allowed to sit in the waiting area for a minimal of 10 minutes to allow for the lenses to settle.
7. Visual acuity with initial contact lens power will be assessed.
 - a. Distance visual acuity
 - i. High Illumination High Contrast (OU)
 - ii. Low Illumination High Contrast (OU)
 - b. Near visual acuity
 - iii. High Illumination High Contrast (OU)
 - iv. Low Illumination High Contrast (OU)
8. After lens settling a standard distant monocular over-refraction will be performed. The endpoint of this over refraction will be the best objective acuity and subjective acuity improvement.
 - a. Up to -0.50D will be given if objective visual acuity is improved.
 - b. -0.25D will be given if subjective visual acuity is significantly improved.
9. A lens change will be implemented if over-refraction dictates. The replacement lens will be allowed to settle for 10 minutes.
10. Change lens prescription to that noted by over-refraction, if needed.
11. Visual Acuity will be assessed with the final lens powers.
 - c. Distance visual acuity
 - v. High Illumination High Contrast (OU)
 - vi. High Illumination Low Contrast (OD, OS, OU)

vii. Low Illumination High Contrast (OD, OS, OU)

d. Near visual acuity

viii. High Illumination High Contrast (OU)

ix. Low Illumination High Contrast (OU)

High Illumination: Overhead lights on, Ideal: 60cd/m², Range: 120-200cd/m²

Low Illumination: Overhead lights off, Ideal: Ideal: 3cd/m², Range: 1-5cd/m²

[REDACTED]

[REDACTED]

14. The subject will be instructed to wear lenses for a minimal of 8 hours/day and every day until the subject come back for the follow-up visit.

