15. The subject will be given enough lenses including spares to last them until the next visit.

16. The subject will be discharged and scheduled to come back for the follow-up visit wearing the study lenses for at least two hours within the required visit window.

17. The subject will be instructed to come back for the follow-up visit wearing the study lenses for at least two hours prior to the visit time.

7.4.3 Visit 2: Follow up lens pair 1/Dispensing lens pair 2 (3 days +2 days from Visit 1)

Subjects should attend wearing the study lenses, which should have been in situ for at least two hours. Subjects who attend without lenses in situ for at least two hours will be rescheduled. The following procedures will be performed (any ocular measurement procedures outlined below will be carried out on each eye):

1. Average Wear Time; Wear Time at visit; Problems and Comments will be recorded.

2. Subjects will return any unworn lenses and problem lenses.

[REDACTED]

[REDACTED]

[REDACTED]

5. Visual Acuity will be assessed with the contact lenses.

a. Distance visual acuity

i. High Illumination High Contrast (OU)

ii. High Illumination Low Contrast (OD, OS, OU)

iii. Low Illumination High Contrast (OD, OS, OU)

- b. Near visual acuity
 - i. High Illumination High Contrast (OU)
 - ii. Low Illumination High Contrast (OU)

High Illumination: Overhead lights on, Ideal: 60cd/m², Range: 120-200cd/m²

Low Illumination: Overhead lights off, Ideal: Ideal: 3cd/m², Range: 1-5cd/m²

6. Monocular over-refraction and High Illumination High Contrast logMAR VA @ 4m (OU) will be performed and recorded.
7. [REDACTED]
8. Lens removal and lens storage.
9. Slit lamp biomicroscopy will be assessed set out in the CVI grading scales.
10. Eyes will be rinsed.
11. The Randomised Pair 2 lenses will be fitted.
12. Initial contact lens power chosen based on vertexed, spherical equivalent obtained from refraction (i.e. match the initial power of the first pair).
13. The initial lens fit will be assessed for fit acceptance (acceptable or not acceptable). If the fit is acceptable, the subject will be allowed to sit in the waiting area for a minimal of 10 minutes to allow for the lenses to settle.
14. Visual acuity with initial contact lens power will be assessed.
 - a. Distance visual acuity
 - i. High Illumination High Contrast (OU)
 - ii. Low Illumination High Contrast (OU)
 - b. Near visual acuity
 - i. High Illumination High Contrast (OU)
 - ii. Low Illumination High Contrast (OU)

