10.1 Statistical analysis

Summary statistics will be produced (e.g. mean, standard deviation). Paired t test will be used to compare slit lamp biomicroscopy, [REDACTED]. Repeated Measures Analysis of Variance (ANOVA) or paired analysis will be used to compare the variables between study visits. The critical alpha level for statistical significance will be set at $p \leq 0.05$, with adjustment for multiple comparisons. Non-inferiory or equivalence testing will be conducted as appropriate.

All participants who were evaluated will be used in the analysis. In the event of missing data, individual data points will be excluded in the analysis and not extrapolated from the collected data.

11 Data Quality Assurance

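### The equivalence analysis takes in all evaluated participants and ignores recorded wear time, so short wear of both lenses can tilt the slit-lamp comparison towards equivalence

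*Combined protocol and SAP*

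**What the plan says.** Section 2.1 sets the primary hypothesis as equivalence: the Test lens "performs substantially equivalent to the MyDay contact lens for ocular health". The secondary hypothesis is non-inferiority for vision.

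Section 10.1 gives one population, "All participants who were evaluated will be used in the analysis", and handles gaps by omission: "individual data points will be excluded in the analysis and not extrapolated from the collected data". Slit-lamp findings are compared by paired t test, and "Non-inferiory or equivalence testing will be conducted as appropriate". The readable text states no margin. The redaction in that section falls in the list of variables for the t test, not in the population sentence.

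On wear, Section 7.2 requires willingness to wear lenses 8 hours daily. Section 7.4.2 (step 14) tells subjects to "wear lenses for a minimal of 8 hours/day and every day", and Section 7.4.3 (step 21) repeats this for the second pair. At both follow-ups (Sections 7.4.3 and 7.4.4, step 1), "Average Wear Time; Wear Time at visit; Problems and Comments will be recorded". A subject whose lenses have been in for less than two hours is rescheduled. Section 11.5.1 has deviations documented and reported but does not tie them to an analysis set.

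**The concern.** Analysing everyone is the cautious choice when the aim is to show a difference, because poor adherence works against the claim. When the aim is to show similarity, it can work for the claim. A subject with little exposure to either lens has little ocular response to either, so the within-subject difference moves towards zero.

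The two-hour rule governs only the day of the visit. Each lens is worn for about three days, so one or two short earlier days are a large share of total exposure and would pass unnoticed by the analysis. At stake is whether a real ocular-health difference at the limit of what is acceptable could be declared equivalent partly because the lenses were not worn as instructed.

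**Working it through.** **The plan's own figure.** Section 7.2 plans up to 80 recruited and about 50 completers. That allows for 1 − 50/80 = 37.5% loss. The 50 itself cannot be reproduced, because the readable text gives no margin, SD, power or dropout rate.

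**Inputs.** From the documents: n = 50 and a paired comparison. Assumed, because the documents give none:
- margin m = 0.5 grade (range 0.25 to 0.5);
- SD of the paired difference s = 0.4 grade (range 0.3 to 0.5);
- two one-sided tests at 5% each (Section 10.1 gives 0.05 without sidedness);
- a fraction f of poor wearers, 10% or 20%;
- a share k of the true difference that poor wearers retain.

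The true difference in compliant wearers is set at the margin, where a sound test should declare equivalence about 5% of the time.

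**Formula.** The expected mean difference falls below the margin by f(1 − k)m. The SD of the mixed sample is √[s² + f(1 − f)(1 − k)²m²]. The chance of false equivalence is approximately Φ(shift ÷ (SD/√50) − 1.645).

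**Half the difference kept (k = 0.5).**
- f = 10%: shift 0.1 × 0.5 × 0.5 = 0.025; SD 0.407; standard error 0.0576; Φ(0.434 − 1.645) = 11.3%.
- f = 20%: shift 0.050; SD 0.412; standard error 0.0583; Φ(0.857 − 1.645) = 21.5%.

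**No difference kept (k = 0, worst case).**
- f = 10%: shift 0.050; SD 0.427; standard error 0.0604; Φ(0.828 − 1.645) = 20.7%.
- f = 20%: shift 0.100; SD 0.447; standard error 0.0632; Φ(1.581 − 1.645) = 47.5%.

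**Simulation with t-based tests (40,000 runs per setting)** agrees closely. The ranges cover the assumed margins and SDs.

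| Poor wearers | Half kept | Half kept, range | None kept | None kept, range |
|---|---|---|---|---|
| 0% | 5% | – | 5% | – |
| 10% | 11% | 7–14% | 20% | 10–27% |
| 20% | 21% | 10–29% | 46% | 17–61% |

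If poor wearers keep three quarters of the difference, the base-case rates are about 8% and 11%.

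**After the fix.** With poor wearers removed (45 or 40 subjects left), the rate at the margin returns to about 5%. This holds in a model where poor wear is unrelated to lens response.

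**The case against.** The case against has four parts.

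*The large figures describe subjects the protocol mostly keeps out.* Slit-lamp examination follows lens removal at a visit that requires two hours of wear, and subjects are current soft-lens wearers willing to wear lenses 8 hours daily. The realistic problem is short wear, not absent wear. This stands. A reader might take 20% and 46% as the expected size; the documents do not support that, and they give no rate of poor wear at all.

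*The direction is not certain.* A difference near zero needs short wear in both periods. Short wear in one period only can move the paired difference either way. Section 8.1 also accepts that transient symptoms may reduce wearing time, so short wear may itself be a response to a lens. Excluding those subjects could remove the ones who reacted. This stands, and it is why a compliant set cannot replace the all-evaluated analysis.

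*Visual acuity is much less exposed.* It is measured with the lenses on the eye, after at least two hours' wear. A reader might extend the bias to the secondary non-inferiority question, but earlier short days have little route to affect it.

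*The missing margin is the larger gap.* It is a separate and prior issue: without a margin, an error rate at the margin is defined only under assumption. That limits the numbers but does not remove the point about the population. Nor should Section 10.1 be read as forbidding a supportive analysis; it names one population and plans no other.

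**Conclusion.** The point holds for the primary slit-lamp comparison. Section 10.1 states a population rule that leaves recorded wear out of an equivalence analysis, and short wear of both lenses tends to favour the equivalence claim. The two-hour rule limits the problem without closing it.

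The size is conditional. With a margin of 0.5 grade, SD 0.4, 50 subjects and one-sided 5% tests, false equivalence at the margin goes from 5% to about 11% and 21% for 10% and 20% poor wearers who keep half the difference. The figures of 20% and 46% are a worst case. Margin, SD, share of poor wearers and retained effect are all assumptions. If wear was good, the two analyses will barely differ. This is a cheap improvement, not a flaw that invalidates the trial.

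**What to change.** Before unmasking, add to Section 10.1 a wear-compliant (per-protocol) set built from the protocol's own requirements: average wear of at least 8 hours a day in both periods, follow-up visits inside the windows of Sections 7.4.3 and 7.4.4, and no eligibility violation. Run the primary slit-lamp equivalence analysis on this set beside the all-evaluated analysis, and claim equivalence only if both agree. For visual acuity, report the compliant-set analysis as supportive only. Report the number excluded and the reasons by lens, so that wear shortened by one lens is visible.

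The cost is one more run of the same analysis on data already collected. The downsides are a smaller second set, a slightly harder success rule, and possible selection bias in the compliant set if short wear is a response to a lens. Because the recorded measure is an average, it can also miss a single short day.

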11.1 Study monitoring

Site qualification of the investigative site has been completed to ensure that the site facility is adequate, personnel are qualified and resources are satisfactory to conduct clinical studies for the Sponsor. The protocol will be reviewed by the investigators prior to enrollment of the first subject. This will involve an overview of the protocol, which includes information on study objectives, inclusion and exclusion criteria, study visits and adverse event reporting. Data collection forms will also be reviewed and this will provide an opportunity to discuss any questions.

During the course of the study, a site visit may be conducted to verify that written informed consent was obtained using the IRB approved ICF prior to each subject's participation in the study.

Prior to final data freeze, a close-out visit/discussion may be warranted to check for accuracy and completeness of records. The sponsor or sponsor's representatives will be authorized to gain access to the source documentation for the purposes of monitoring and auditing the study.

11.2 Record keeping

Detailed records of all study visits will be made using the Case Report Forms (CRFs). All data recorded on forms will be in ink. Any corrections to the forms will be initialed and dated at the time they are modified.

11.3 Record retention

Following study completion, data will be available in electronic and/or paper format for audit, sponsor use, or subsequent analysis. The original clinical raw data (including completed CRFs and Informed Consent forms) will be retained according to guidelines set forth in the general work agreement with the site. The Sponsor will be notified and consulted if ever the files are to be destroyed. In the event that this implementation document is indicated for design verification and validation purposes, as indicated on the title page, all original raw data forms and completed CRF's will be forwarded to the sponsor at completion of the final report.

11.4 Data Entry / Data Management

Data will be entered into an electronic spreadsheet. Study staff will only be able to modify the data file via password entry. The investigators will be responsible for the data integrity, and complete data entry for each visit as. The investigator will send the data collected to the study sponsor within approximately 5 business days after the last subject completes the final visit.

11.5 Protocol Deviations

Protocol deviations are unanticipated or unintentional changes to a study after it has received prior sponsor approval and ethics clearance. Protocol deviations can be major or minor.

Major protocol deviations may impact the research protocol, Informed Consent form or other study materials, usually cannot be anticipated ahead of time and are often necessary to ensure the safety and welfare of the subjects.

The following are examples of protocol deviations that must be reported to the IRB:

1. Changes in procedures initiated to eliminate immediate risks/hazards to subjects;
2. Enrolment of subjects outside the protocol inclusion/exclusion criteria;
3. Inadvertent deviation in specific research intervention procedures or timing of the research intervention which could impact upon the safety or efficacy of the study-related intervention or upon the experimental design;

4. Informed Consent documentation violations: no documentation of informed consent; incorrect version of, or incomplete, informed consent documentation used.

Minor protocol deviations are caused by or which originate with research subjects and normally are not reported to the IRB unless these result in increased risk to the subjects(s). The following are examples of protocol deviations that are considered minor and do not require reporting to the IRB:

- Logistical or administrative aspects of the study (e.g., study subject missed appointment, change in appointment date or time);
- Inadvertent deviation in specific research intervention procedures or timing of the research intervention which would not impact upon the safety or efficacy of the study-related intervention or upon the experimental design (i.e., missing a measurement during a session that is not considered critical for the study).

11.5.1 Reporting and documenting protocol deviations

Major protocol deviations which require changes to the research protocol or informed consent process/document or other corrective actions to protect the safety, welfare, or rights of patients or others must be reported to the IRB according to the site's guidelines. All protocol deviations (major and minor) occurring during the study will be documented and included in the final report and data safety monitoring report to the IRB

11.7 Publication

Indiana University may publish the results of this study, subject to the conditions laid out in the CooperVision Master Services Research Agreement, dated 20 June 2007.

12 Study Costs

The sponsor will compensate the clinical site and the subjects for their time and participation in this voluntary study.

Expenses incurred for medical treatment as part of study participation will be paid by the sponsor (bills and prescription receipts kept). The participant must be followed until resolution and a written report completed indicating the subsequent treatment and resolution of the condition.

13 Appendices

Appendix 1 Randomization Table

Appendix 2 CVI Grading Scales

Appendix 3 Questionnaires

APPENDIX 1

A large table with 10 columns and approximately 30 rows. The table is almost entirely redacted with black bars. The top row has a blue header, and the first column has a black header. The remaining cells are obscured by black bars.

APPENDIX 2

| [REDACTED] | | |
|--|--|--|
| [REDACTED] | | |
| [REDACTED] [REDACTED] | [REDACTED] [REDACTED] [REDACTED] [REDACTED] | [REDACTED] [REDACTED] [REDACTED] [REDACTED] [REDACTED] |
| [REDACTED] [REDACTED] [REDACTED] [REDACTED] | [REDACTED] [REDACTED] [REDACTED] [REDACTED] [REDACTED] [REDACTED] [REDACTED] [REDACTED] [REDACTED] | [REDACTED] [REDACTED] [REDACTED] [REDACTED] [REDACTED] [REDACTED] [REDACTED] |
| [REDACTED] [REDACTED] [REDACTED] [REDACTED] | [REDACTED] [REDACTED] [REDACTED] [REDACTED] [REDACTED] | [REDACTED] [REDACTED] [REDACTED] [REDACTED] [REDACTED] |

| | | |
|------------|------------|------------|
| [REDACTED] | [REDACTED] | [REDACTED] |
| [REDACTED] | [REDACTED] | [REDACTED] |
| [REDACTED] | [REDACTED] | [REDACTED] |
| [REDACTED] | [REDACTED] | [REDACTED] |

| | | |
|--|--|--|
| [REDACTED] [REDACTED] [REDACTED] [REDACTED] [REDACTED] | [REDACTED] [REDACTED] [REDACTED] [REDACTED] [REDACTED] [REDACTED] [REDACTED] [REDACTED] | [REDACTED] [REDACTED] [REDACTED] [REDACTED] [REDACTED] |
| [REDACTED] [REDACTED] | [REDACTED] [REDACTED] [REDACTED] [REDACTED] [REDACTED] | [REDACTED] [REDACTED] [REDACTED] [REDACTED] [REDACTED] |
| [REDACTED] | [REDACTED] [REDACTED] [REDACTED] [REDACTED] [REDACTED] | [REDACTED] [REDACTED] [REDACTED] |
| [REDACTED] [REDACTED] [REDACTED] [REDACTED] | [REDACTED] [REDACTED] [REDACTED] [REDACTED] [REDACTED] [REDACTED] [REDACTED] [REDACTED] [REDACTED] | [REDACTED] [REDACTED] [REDACTED] [REDACTED] [REDACTED] |

| | | |
|--|--|--|
| [REDACTED] [REDACTED] | [REDACTED] [REDACTED] | [REDACTED] [REDACTED] |
| [REDACTED] [REDACTED] [REDACTED] | [REDACTED] [REDACTED] [REDACTED] [REDACTED] [REDACTED] [REDACTED] | [REDACTED] [REDACTED] [REDACTED] [REDACTED] [REDACTED] |
| [REDACTED] [REDACTED] [REDACTED] | [REDACTED] [REDACTED] [REDACTED] [REDACTED] [REDACTED] [REDACTED] | [REDACTED] [REDACTED] [REDACTED] [REDACTED] [REDACTED] |

| [Redacted] | | |
|------------|------------|------------|
| [Redacted] | [Redacted] | [Redacted] |
| [Redacted] | [Redacted] | [Redacted] |

| | | |
|--|--|--|
| [REDACTED] [REDACTED] [REDACTED] [REDACTED] | [REDACTED] [REDACTED] [REDACTED] | [REDACTED] [REDACTED] [REDACTED] [REDACTED] [REDACTED] [REDACTED] [REDACTED] [REDACTED] |
| [REDACTED] [REDACTED] [REDACTED] [REDACTED] | [REDACTED] [REDACTED] | [REDACTED] [REDACTED] [REDACTED] [REDACTED] |
| [REDACTED] [REDACTED] [REDACTED] [REDACTED] | [REDACTED] [REDACTED] | [REDACTED] [REDACTED] [REDACTED] [REDACTED] [REDACTED] [REDACTED] |
| [REDACTED] [REDACTED] [REDACTED] | [REDACTED] [REDACTED] [REDACTED] [REDACTED] [REDACTED] [REDACTED] | [REDACTED] [REDACTED] [REDACTED] [REDACTED] [REDACTED] |

| | | |
|--|--|--|
| [REDACTED] [REDACTED] [REDACTED] [REDACTED] | [REDACTED] [REDACTED] [REDACTED] [REDACTED] [REDACTED] [REDACTED] | [REDACTED] [REDACTED] [REDACTED] [REDACTED] [REDACTED] [REDACTED] [REDACTED] |
| [REDACTED] [REDACTED] [REDACTED] | [REDACTED] [REDACTED] [REDACTED] [REDACTED] [REDACTED] [REDACTED] | [REDACTED] [REDACTED] [REDACTED] |
| [REDACTED] [REDACTED] [REDACTED] [REDACTED] | [REDACTED] [REDACTED] [REDACTED] [REDACTED] [REDACTED] [REDACTED] [REDACTED] [REDACTED] | [REDACTED] [REDACTED] [REDACTED] [REDACTED] [REDACTED] [REDACTED] |
| [REDACTED] [REDACTED] [REDACTED] [REDACTED] | [REDACTED] [REDACTED] [REDACTED] [REDACTED] [REDACTED] [REDACTED] | [REDACTED] [REDACTED] [REDACTED] |

[REDACTED]

[REDACTED]

| | | | | | |
|------------|------------|------------|------------|------------|------------|
| [REDACTED] | [REDACTED] | [REDACTED] | [REDACTED] | [REDACTED] | [REDACTED] |
| [REDACTED] | [REDACTED] | [REDACTED] | [REDACTED] | [REDACTED] | [REDACTED] |
| [REDACTED] | [REDACTED] | [REDACTED] | [REDACTED] | [REDACTED] | [REDACTED] |
| [REDACTED] | [REDACTED] | [REDACTED] | [REDACTED] | [REDACTED] | [REDACTED] |
| [REDACTED] | [REDACTED] | [REDACTED] | [REDACTED] | [REDACTED] | [REDACTED] |
| [REDACTED] | [REDACTED] | [REDACTED] | [REDACTED] | [REDACTED] | [REDACTED] |
| [REDACTED] | [REDACTED] | [REDACTED] | [REDACTED] | [REDACTED] | [REDACTED] |
| [REDACTED] | [REDACTED] | [REDACTED] | [REDACTED] | [REDACTED] | [REDACTED] |

[Redacted]

[Redacted]

| | | | | | |
|------------|------------|------------|------------|------------|------------|
| [Redacted] | [Redacted] | [Redacted] | [Redacted] | [Redacted] | [Redacted] |
| [Redacted] | [Redacted] | [Redacted] | [Redacted] | [Redacted] | [Redacted] |
| [Redacted] | [Redacted] | [Redacted] | [Redacted] | [Redacted] | [Redacted] |
| [Redacted] | [Redacted] | [Redacted] | [Redacted] | [Redacted] | [Redacted] |
| [Redacted] | [Redacted] | [Redacted] | [Redacted] | [Redacted] | [Redacted] |
| [Redacted] | [Redacted] | [Redacted] | [Redacted] | [Redacted] | [Redacted] |
| [Redacted] | [Redacted] | [Redacted] | [Redacted] | [Redacted] | [Redacted] |

[REDACTED]

[REDACTED]

| | | | | |
|------------|------------|------------|------------|------------|
| [REDACTED] | [REDACTED] | [REDACTED] | [REDACTED] | [REDACTED] |
| [REDACTED] | [REDACTED] | [REDACTED] | [REDACTED] | [REDACTED] |
| [REDACTED] | [REDACTED] | [REDACTED] | [REDACTED] | [REDACTED] |
| [REDACTED] | [REDACTED] | [REDACTED] | [REDACTED] | [REDACTED] |

[REDACTED]

| | | | | |
|------------|------------|---|------------|------------|
| [REDACTED] | [REDACTED] |] | [REDACTED] | [REDACTED] |
| | [REDACTED] |] | [REDACTED] | [REDACTED] |
| | [REDACTED] |] | [REDACTED] | [REDACTED] |
| | [REDACTED] | | [REDACTED] | [REDACTED] |
| | [REDACTED] | | [REDACTED] | [REDACTED] |
| | [REDACTED] |] | [REDACTED] | [REDACTED] |
| | [REDACTED] |] | [REDACTED] | [REDACTED] |
| | [REDACTED] |] | [REDACTED] | [REDACTED] |

| | | | |
|------------|------------|------------|------------|
| [REDACTED] | [REDACTED] | [REDACTED] | [REDACTED] |
| | [REDACTED] | | [REDACTED] |
| | [REDACTED] | | [REDACTED] |
| [REDACTED] | [REDACTED] | | [REDACTED] |
| | [REDACTED] | | [REDACTED] |
| | [REDACTED] | | [REDACTED] |
| [REDACTED] | [REDACTED] | | [REDACTED] |

| | | | |
|------------|------------|------------|------------|
| [REDACTED] | | | |
| [REDACTED] | [REDACTED] | [REDACTED] | [REDACTED] |
| [REDACTED] | [REDACTED] | [REDACTED] | [REDACTED] |
| [REDACTED] | | | |

| | | | | |
|------------|------------|------------|------------|------------|
| [REDACTED] | | | | |
| [REDACTED] | | | | |
| [REDACTED] | [REDACTED] | [REDACTED] | [REDACTED] | [REDACTED] |
| [REDACTED] | [REDACTED] | [REDACTED] | [REDACTED] | [REDACTED] |
| [REDACTED] | | | | |
